5.9 Data and specimen sharing/banking. Do you plan to share some or all of the data, specimens, or subject contact information with other researchers or a repository/database, or to bank them for your own future unspecified research uses? **You are strongly encouraged to consider the broadest possible future plans you might have, and whether you will obtain consent now from the subjects for future sharing or unspecified uses.** Answer **NO** if your only sharing will be through the NIH Genomic Data Sharing described in [question 5.8](#).

Many federal grants and contracts now require data or specimen sharing as a condition of funding, and many journals require data sharing as a condition of publication. “Sharing” may include: informal arrangements to share your banked data/specimens with other investigators; establishing a repository from which you formally share with others through written agreements; or sending your data/specimens to a third party repository/archive/entity such as the NIH dbGaP database, the Social Science Open Access Repository (SSOAR), or the UCLA Ethnomusicology Archive.

No

Yes

→ If yes, answer all of the questions below.

a. Describe what will be stored, including whether any direct or indirect (e.g., subject codes) identifiers will be stored.

b. Describe what will be shared, including whether direct identifiers will be shared and (for specimens) what data will be released with the specimens.

c. Who will oversee and/or manage the sharing?

d. Describe the possible future uses, including limitations or restrictions (if any) on future uses or users. As stated above, consider the broadest possible uses.

Examples: data will be used only for cardiovascular research; data will not be used for research on population origins.

e. Consent. Will you obtain consent now from subjects for the banking and/or future sharing?

	No
	Yes

→ If yes, be sure to include the information about this consent process in the consent form (if there is one) and in your answers to the consent questions in [Section 6](#).

f. Withdrawal. Will subjects be able to withdraw their data/specimens from banking or sharing?

	No
	Yes

→ If yes, describe how, and whether there are any limitations on withdrawal.

Example: data can be withdrawn from the repository but cannot be retrieved after they are released.

g. Agreements for sharing or release. Confirm by checking the box that you will comply with UW (and, if applicable, UW Medicine) policies that require a formal agreement between you and the recipient for release of data or specimens to individuals or entities other than federal databases.

Data Use Agreements or Gatekeeping forms are used for data; Material Transfer Agreements are used for specimens (or specimens plus data). Do not attach your template agreement forms; the IRB neither reviews nor approves them

Confirmed

5.10 Communication with subjects during the study. Describe the types of communication (if any) you will have with already-enrolled subjects during the study. Provide a description instead of the actual materials themselves.

Examples: email, texts, phone, or letter reminders about appointments or about returning study materials such as a questionnaire; requests to confirm contact information.

We anticipate conducting the exit interviews with FP clinic staff that we have been working with throughout the randomized clinical trial (and whom we interviewed previously for HIV counseling and testing practices). Study staff will text or call FP clinic staff and see if they are available to spend approximately 1 hour with our staff to answer some questions about SAIA. Written informed consent will be obtained.

In the event that social distancing prevents participants from signing the written informed consent document, the consent process will be over the phone with study staff reading the consent document.

5.11 Future contact with subjects. Do you plan to retain any contact information you obtain for your subjects so that they can be contacted in the future?

	No
	Yes

→ If yes, describe the purpose of the future contact, and whether use of the contact information will be limited to your team; if not, describe who else could be provided with the contact information. Describe your criteria for approving requests for the information.

Examples: inform subjects about other studies; ask subjects for additional information or medical record access that is not currently part of the study proposed in this application; obtain another sample.

5.12 Alternatives to participation. Are there any alternative procedures or treatments that might be advantageous to the subjects?

If there are no alternative procedures or treatments, select "No". Examples of advantageous alternatives: earning extra class credit in some time-equivalent way other than research participation; obtaining supportive care or a standard clinical treatment from a health care provider instead of participating in research with an experimental drug.

	No
	Yes

→ If yes, describe the alternatives.

5.13 Upload to the Supporting Documents SmartForm of **Zipline** all data collection forms (if any) that will be directly used by or with the subjects, and any scripts/talking points you will use to collect the data. Do not include data collection forms that will be used to abstract data from other sources (such as medical or academic records, or video recordings).

- **Examples:** survey, questionnaires, subject logs or diaries, focus group questions.
- **NOTE:** Sometimes the IRB can approve the general content of surveys and other data collection instruments rather than the specific form itself. This prevents the need to submit a modification request for future minor changes that do not add new topics or increase the sensitivity of the questions. To request this general approval, use the text box below to identify the questionnaires/surveys/ etc. for which you are seeking this more general approval. Then briefly describe the scope of the topics you will cover and the most personal and sensitive questions. The HSD staff person who screens this application will let you know whether this is sufficient or whether you will need to provide more information.
- **For materials that cannot be uploaded:** upload screenshots or written descriptions that are sufficient to enable the IRB to understand the types of data that will be collected and the nature of the experience for the participant. You may also provide URLs (website addresses) or written descriptions below. Examples of materials that usually cannot be uploaded: mobile apps; computer-administered test; licensed and restricted standardized tests.
- **For data that will be gathered in an evolving way:** This refers to data collection/questions that are not pre-determined but rather are shaped during interactions with participants in response to observations and responses made during those interactions. If this applies to your research, provide a description of the process by which you will establish the data collection/questions as you interact with subjects, how you will document your data collection/questions, the topics you plan to address, the most sensitive type of information you will plan to gather, and the limitations (if any) on topics you will raise or pursue.

Use this text box (if desired) to provide:

- Short written descriptions of materials that cannot be uploaded, such as URLs
- A description of the process you will use for data that will be gathered in an evolving way.
- The general content of questionnaires, surveys and similar instruments for which you are seeking general approval. (See the **NOTE** bullet point in the instructions above.)

Minor changes may be made to the *Key Informant Interview Guide for Family Planning Clinic Staff* without submitting the materials for IRB review as long as the changes are within the scope and range of the current topics.

The exit interview guide includes questions about acceptability, appropriateness, feasibility, and complexity of SAIA. The draft of the interview guide has been uploaded to Zipline.

5.14 Send HSD a [Confidentiality Agreement](#) if you will obtain or use any private identifiable UW records without subject's written consent (for example, screening medical records or class grades to identify possible subjects).

The Confidentiality Agreement form must be completed, printed, signed, and mailed to the Human Subjects Division at Box 359470. Your IRB application cannot be approved until we receive the Confidentiality Agreement.

6 CHILDREN (MINORS) and PARENTAL PERMISSION

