5 PROCEDURES

5.1 Study procedures. Using lay language, provide a complete description of the study procedures, including the sequence, intervention or manipulation (if any), time required, and setting/location. If it is available and you think it would be helpful to the IRB: Upload a study flow sheet or table to the **Supporting Documents** SmartForm in **Zipline**.

For studies comparing standards of care: It is important to accurately identify the research procedures. See UW IRB [POLICY: Risks of Harm from Standard Care](#) and the draft guidance from the federal Office of Human Research Protections, ["Guidance on Disclosing Reasonably Foreseeable Risks in Research Evaluating Standards of Care"](#); October 20, 2014.

Preliminary Performance Review

The initial step will include a performance review of 50 FP clinics, purposively sampled to include a range of large and small, public and private, urban, peri-urban, and rural facilities. We will use routinely reported data in the FP Registers to measure the proportion of new clients counselled and tested for HIV. These data will be used to assign a performance score to each clinic, as shown in [Figure 6](#). This will also help to confirm that different clinics are using the same registers. If multiple registers are identified, then we will keep records of the different versions that exist and compare between registers when able.

Figure 6: Definitions & Calculation of Performance Score Using Data from FP Register

HIV Counseling	Numerator: Number of new FP clients counselled about HIV testing in the past 3 months Denominator: Total number of new FP clients in the past 3 months	Score 1
HIV Testing	Numerator: Number of eligible (not known HIV+) new FP clients tested for HIV in the past 3 months Denominator: Total number of eligible (not known HIV+) new FP clients in the past 3 months	Score 2
Overall Performance	Score 1 X Score 2: The product of the two proportions will fall on a 0-100 distribution	Score 3

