We will evaluate the association between facilities' characteristics and performance scores, both overall and for the individual *HIV Counseling* and *HIV Testing* components (52). Results will be interpretable as showing that facility factor 'x' is associated with 'y' percent more women getting through counseling, testing, or both. With this small dataset, we are not focused on statistical significance. Instead, we will be interested in the magnitude of associations and triangulation with our qualitative data and observations. Qualitative data will be analyzed from the interview notes and recordings, using a rapid assessment approach to identify recurring themes. The quantitative data, qualitative data, and flow maps will be summarized in a report that highlights performance facilitators and barriers. We will then review the data with FP managers and staff to identify unique innovations and draft an intervention guide including best practices to guide the subsequent steps. Given variations between facility types, there may be more than one set of best practices.

Step 1: Understanding the cascade from FP clinic enrollment to HIV testing. The purpose of this step is to help clinic staff and managers to answer the questions, “What are we trying to accomplish?”, and, “How will we know that a change is an improvement?” (53). Using readily available data from the FP Register, we will determine the number of new FP clients enrolled, counselled about HIV testing, and tested for HIV. To facilitate systems thinking, we will utilize a Microsoft Excel-based tool like the one that is currently being used in the *SAIA Trial*. While the present tool is not easily converted to a figure, an earlier and less detailed version used for studies in Mozambique highlights many of the key features of the cascade analysis tool (Figure 7) (55). Specifically, the tool demonstrates patient flow through the system, highlighting bottlenecks where patients are lost and calculating the potential increase in efficiency if loss were reduced or eliminated at each step, assuming that all other steps are held constant (55).

Step 2: Use process mapping to identify modifiable bottlenecks. This step compels FP clinic staff and managers to address the question, “What change can we make that will result in improvement (53)?” Aided by the process map clinics will identify one or more processes to target for improvement.

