Step 3: Define and implement workflow adaptations to eliminate modifiable bottlenecks. This step will involve development of a written implementation plan addressing the questions, “Who will be responsible for implementing the intervention?”, “What activities will be initiated?” and “What materials/inputs are needed for the intervention?” (56). Small costs for materials/inputs can be covered from the grant budget and tracked for the costing and budget impact analysis. Interventions will be conceived by clinic staff and management with support from study staff using a combination of best practices from the intervention guide and context specific adaptations based on strengths and challenges at individual facilities.

Step 4: Monitor change in performance. The goal of this step is for staff and managers to effectively use routinely collected data to understand the impact of workflow adaptations on the movement of patients through the system. Data from one to two months will be evaluated using the Excel-based tool introduced in *Step 1*. A graphic time-series display of key outcome data will be created to visually depict improvements.

Step 5: Repeat the analysis and improvement cycle (steps 1-4). This step reflects the concept that workflow quality improvement is a continuous and iterative process, with each new cycle of innovation, testing, and learning building on prior cycles (53). Multiple cycles will be completed over a period of 12 months.

At control clinics, we will collect the same information from the FP register as the intervention arm (contraceptive method, age, client type, HIV counselling, HIV tested and HIV status), periodically, but not more often than every three months. We do not want to collect these too frequently, as this observation alone might have some intervention impact on the control clinics (Hawthorne Effect).

[figure not shown]

Figure 7. Example of Microsoft Excel-based analysis tool for identifying facility-level bottlenecks in the care cascade

Randomization:

Randomization will be performed by a statistician from our CFAR biometrics core, who does not have any other role in this study. We will use a restricted randomization that considers all possible combinations where the clusters are balanced on new client volume and performance score, then randomly selects one of these combinations as the randomization. This allows analysis of the data as if they were unmatched.

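### Section 5.1 reads the overall performance score as a share of women completing both steps, which it is not; separately, the Section 5.2 GEE on 24 clinics names no small-sample method

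*Combined protocol and SAP*

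**What the plan says.** **Scores.** In Figure 6 (Section 5.1), the counselling score (Score 1) has "Denominator: Total number of new FP clients in the past 3 months". The testing score (Score 2) has "Denominator: Total number of eligible (not known HIV+) new FP clients in the past 3 months"; it is not restricted to women who were counselled. The overall score (Score 3) is "Score 1 X Score 2: The product of the two proportions will fall on a 0-100 distribution".

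**Use of the scores.** Under the analysis of the detailed review of intervention clinics, the plan relates facility "characteristics and performance scores, both overall and for the individual" counselling and testing components. It says a factor will be interpretable as giving some "percent more women getting through counseling, testing, or both". It adds "With this small dataset, we are not focused on statistical significance" and puts the interest in the size of the associations. Step 1 of the intervention says "we will determine the number of new FP clients enrolled, counselled about HIV testing, and tested for HIV". The register fields abstracted in both arms are "contraceptive method, age, client type, HIV counselling, HIV tested and HIV status".

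**Primary analysis.** Section 1.5 gives 12 intervention and 12 control clinics. Section 5.2 plans an intent-to-treat GEE clustered by clinic, for testing and for counselling. It describes the link only as binary and names no covariates, working correlation, variance estimator, degrees of freedom or small-sample correction. Under Randomization in Section 5.1, allocation is restricted to balance new client volume and performance score, and the data may then be analysed as unmatched.

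**The concern.** Three scores are analysed (counselling, testing, overall) and three readings are offered (counselling, testing, or both), so *both* most naturally attaches to the overall score. A product of two marginal proportions does not in general give the proportion of women who completed both steps. A factor that changes only counselling could then be reported as moving more women through the whole cascade, and that could feed into the best-practice guide.

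The second matter concerns the trial result. With 24 clusters, a GEE with the usual sandwich standard error and a normal reference tends to reject too often. Section 5.2 does not rule that choice out, so the false-positive rate for HYP 1 and HYP 2 is left open.

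**Working it through.** The documents state no alpha, power, ICC or target effect, so there is no design figure to reproduce.

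**Part 1: the overall score.** Let a be the proportion counselled and b the proportion tested, first on one common denominator. Score 3 = a × b. The share completing both can lie anywhere from max(0, a + b − 1) to min(a, b).

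| Counselled | Tested | Score 3 | Possible share completing both |
|---|---|---|---|
| 50% | 40% | 20 | 0-40% |
| 60% | 40% | 24 | 0-40% |
| 80% | 20% | 16 | 0-20% |
| 40% | 40% | 16 | 0-40% |
| 80% | 70% | 56 | 50-70% |

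Suppose every tested woman was counselled, as a counsel-then-test cascade suggests. The share completing both is then b itself, and multiplying by a counts the counselling loss twice:

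- At b = 40%, moving a from 50% to 60% raises Score 3 from 20 to 24. The share stays at 40%.
- At a = 50%, moving b from 40% to 50% raises Score 3 by 5 points (20 to 25). The share rises by 10 (40% to 50%).
- Clinics at 60/30 and 30/30 both have 30% completing both, but score 18 and 9.

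The denominators also differ. Assume that 2-10% of new clients are known HIV-positive and are not counselled (an assumption; the documents give neither figure). A clinic that counsels and tests every eligible woman then scores 98 to 90, not 100.

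**Part 2: type I error with 24 clinics.** The reference distribution alone matters: with an exact standard error and t-distributed statistics on 22 df (critical value 2.074), a z-test has size 6.3%. Downward bias of the sandwich standard error adds to this. Two simulations, both 12 v 12, logit link, two-sided 5%, clinic SD 1 on the logit scale:

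- *Simulation A:* volume lognormal with mean 21 new clients per month (Section 2.1) and log-SD 0.8; 3-month windows; follow-up testing median 20-30%. Allocation is drawn from the best 10% of 200 on log volume and Score 3. Adjusted models use Score 2 and log volume (20 df). The correlation r of true clinic rates is 0 to 0.7; 3,000 trials per cell.
- *Simulation B:* about 63 clients per clinic (21 × 3); testing 20% or 40%; unrestricted and restricted allocation. One covariate, the baseline testing rate (22 df unadjusted, 21 adjusted). Correlation 0 to 0.8; 2,000 null trials per cell.

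| Setting | Uncorrected SE, z | Mancl-DeRouen SE, t |
|---|---|---|
| A, independence, unadjusted | 7.8-12.6% | – |
| A, independence, adjusted | 13.1-15.3% | 3.4-4.4% |
| A, exchangeable, unadjusted | 3.8-9.6% | – |
| A, exchangeable, adjusted | 9.1-11.5% | 3.1-4.5% |
| B, independence, unrestricted, unadjusted | 9.4-11.2% | 4.5-5.7% |
| B, independence, restricted, unadjusted | 4.0-10.9% | 1.2-5.3% |
| B, independence, adjusted | 10.0-12.8% | 3.8-5.4% |

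The low ends of the restricted, unadjusted row in B arise at correlation 0.8: uncorrected 4.0-5.4%, corrected 1.2-2.4%. Kauermann-Carroll with t leaves the adjusted GEE at 5.7-8.5% across both simulations.

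**Adjustment within the corrected GEE (A).** Interval width relative to unadjusted, at r = 0 / 0.3 / 0.5 / 0.7:

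- independence: 1.06 / 1.03-1.06 / 0.97-1.02 / 0.87-0.96
- exchangeable: 1.08-1.09 / 1.06-1.07 / 1.01-1.05 / 0.92-1.00

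In B, corrected power for an illustrative 20% v 35% under restricted allocation, unadjusted v adjusted, is 29% v 27%, 29% v 31%, 27% v 35% and 24% v 51% at correlations 0, 0.3, 0.6 and 0.8.

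**Input caveat.** The mean of 21 does not follow from the totals in Section 2.1: 38,418 / 194 / 12 = 16.5. With a window of 1 or 12 months or a volume log-SD of 0.5 or 1.1, the pattern in A holds (adjusted, independence: uncorrected 10.3-18.5%, corrected 2.8-4.5%).

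**The case against.** **On the score.** The issue is one word in one sentence. The component scores are reported beside the overall score, so unchanged testing would be visible. Significance is disclaimed, qualitative data are used alongside, and Step 1 counts the cascade. This stands as a limit on the stakes. It does not rescue the reading: magnitude is exactly what the analysis reports, and Step 1's totals give the joint share only if all tested women were counselled. Section 5.2 treats blank fields as not done, which can break that nesting in the records. The review also opens Aim 1, and Aim 2 began in February 2020, so a wording change probably reaches only the reporting.

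A reader might infer that the score is miscalculated or the randomization unsound. The documents do not support that. Figure 6's arithmetic is correct, an index is a legitimate balancing variable, and the primary outcome is the testing proportion, not Score 3.

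**On the GEE.** The plan does not say it will use an uncorrected standard error; silence is not a stated error. That stands. Balanced allocation can also offset the inflation: where the balanced score is strongly prognostic, the uncorrected unadjusted test is near nominal and the corrected one conservative. That stands too, but it relies on a correlation nobody has stated. The remark on unmatched analysis concerns matching, not the number of clusters.

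A reader might infer that omitting baseline covariates is an error or biases the comparison. It is neither: the unadjusted comparison is unbiased, and adjustment is a choice about precision. Nor is small-sample inflation created by adjustment, since it affects the unadjusted GEE as well.

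**Conclusion.** The score reading is wrong as written and of low consequence. Only Scores 1 and 2 can be read as percentages of women; Score 3 is an index. At 50% counselled and 40% tested it is 20, while the share completing both may be anything from 0 to 40%. The error touches the descriptive review of the 12 intervention clinics and its guide, not the trial result.

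The missing small-sample method is a gap that is cheap to close, not a demonstrated error. If an uncorrected standard error and z reference were used, type I error could be about 8-13% unadjusted and 13-15% with two covariates (independence working correlation). These figures rest on assumed clinic variation, volumes and testing rates and on a logit link, and should be read as orders of magnitude.

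Baseline adjustment pays in the corrected GEE only from a correlation of about 0.5 under independence, and nearer 0.7 with exchangeable working correlation. Replacing the primary analysis with a clinic-level linear model is not warranted: it would weight clinics rather than clients and change the effect scale.

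Overall severity: minor.

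**What to change.** **Section 5.1, analysis of the detailed review (two sentences, no new data).** Limit the percent-more-women reading to Scores 1 and 2 and call Score 3 an index. For both steps, count directly the proportion of eligible new clients recorded as counselled and tested. If the review is complete, apply this to its reporting. Leave the balancing on Score 3 as it is.

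**Section 5.2 (about two sentences, no new data).** Keep the GEE and prespecify a Mancl-DeRouen standard error with a t reference on 22 df for the unadjusted model, whether or not covariates are added. The cost is somewhat wider intervals, and a conservative test if the balanced score is strongly prognostic. In simulation B at zero correlation, power for 20% v 35% is 29% corrected against 40% uncorrected, but the uncorrected test has a type I error of 10.9%.

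**Optional.** Adjust for clinic-level baseline testing and log new client volume (20 df), only together with that correction. The price is intervals about 6-9% wider if baseline does not predict follow-up.

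**Timing.** If Aim 1 has already been analysed, keep its result and report the corrected analysis as a labelled sensitivity analysis.

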While HIV testing in new clients is our primary outcome, we feel that a performance score incorporating both counseling and testing may provide a better baseline measure of performance. Nonetheless, we will also consider the individual *HIV Counseling* and *HIV Testing* scores if they do not tend to track together, and will adapt our randomization accordingly. If too few clinics perform any HIV counseling or testing, we will choose alternative measures of performance in the FP Register, such as recording of client number, client type (new/revisit), age, telephone number, and village/landmark. The rationale for conducting this initial step in 50 clinics, rather than just the 24 needed for completion of the RCT, is to provide a larger sample to enter the restricted randomization process. Preliminary examination of these data will allow us to fine-tune our choice of variables on which to balance the study arms and to optimize the planned length of outcome evaluation periods to capture sufficient endpoints. If any clinics seem inappropriate for participation (e.g. planned closure or unmatchable outliers), they may be removed prior to the randomization.

Aim 1:

In the 12 intervention facilities, the study team will first work with FP clinic staff and managers to identify one or more sets of best practices, which will help to guide the subsequent iterative process improvement steps. A combination of quantitative, qualitative, observation, and flow-mapping data will be used for this purpose

Quantitative data: We will collect data on health system factors that could influence facility performance. We will develop a standardized reporting form, refining assessment items according to current implementation experience, but expect to cover domains including commodities, facility characteristics, human resources, information systems, management, and structure of linkage to HIV

care.

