Disclaimer: Due to restrictions on human subject research as a result of the COVID-19 pandemic, most activities for Aim 2, which began in February 2020, were on hold between March and August 2020. Activities resumed in September 2020, but were interrupted again by a strike, in response to unpaid wages and lack of PPE in the context of the COVID-19 pandemic. This has led to a number of our FP clinics being unable to participate in the trial for portions of the original 12-month period described in the Aims and Study Procedures. As a result, Aim 2 data collection will be extended an additional 6 months, for a total of 18 months of data collection for Aim 2.

5.2 Data variables. Describe the specific data you will obtain (including a description of the most sensitive items). If you would prefer, you may upload a list of the data variables to the **Supporting Documents** SmartForm instead of describing the variables below.

The primary outcome will be the proportion of eligible (not known HIV+) new FP clients who are tested for HIV during the evaluation periods at the end of 12 months of SAIA training and following an additional year in which intervention clinics are encouraged to continue to implement the SAIA intervention with minimal support from the study team. The secondary outcome will be the proportion of new FP clients who are counseled about HIV testing. When data are not filled, we will assume the counseling or testing has not been done. While we recognize that there are few variables available in implementation research datasets (e.g. clinic size, public/private, rural/urban), these variables will be collected for comparison of the randomization arms to assess balance across intervention groups.

Our primary analysis will follow the intent-to-treat principle. The proportion of eligible new FP clients tested for HIV and the proportion of new FP clients counselled about HIV testing will be compared in intervention versus control facilities using generalized estimating equations with a binary link, clustered by clinic. Because there will be more than a year between the first and second assessments, we anticipate that these will take place as separate analyses, as they are completed.

5.3 Data sources. For all types of data that you will access or collect for this research: Identify whether you are obtaining the data from the subjects (or subjects' specimens) or whether you are obtaining the data from some other source (and identify the source).

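### The default randomization balances arms on counseling × testing, not on baseline HIV testing itself; the cost is a modest loss of precision, and baseline testing is not in the model

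*Combined protocol and SAP*

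**What the plan says.** **Balancing variables.** Section 5.1 (Randomization) uses a restricted scheme that "considers all possible combinations where the clusters are balanced on new client volume and performance score" and draws one allocation from that set. It gives no balance tolerance.

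**Definition of the score.** In Figure 6, Score 1 is the counseling proportion, with numerator "Number of new FP clients counselled about HIV testing in the past 3 months". Score 2 is the testing proportion, with numerator "Number of eligible (not known HIV+) new FP clients tested for HIV in the past 3 months". The performance score is "Score 1 X Score 2: The product of the two proportions will fall on a 0-100 distribution".

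**Reason and flexibility.** Under Preliminary Performance Review the plan acknowledges that testing is the primary outcome, but says "we feel that a performance score incorporating both counseling and testing may provide a better baseline measure of performance". It will also consider the individual "scores if they do not tend to track together, and will adapt our randomization accordingly", and will use the preliminary data to "fine-tune our choice of variables on which to balance the study arms".

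**Outcome and analysis.** Section 5.2: "The primary outcome will be the proportion of eligible (not known HIV+) new FP clients who are tested for HIV during the evaluation periods". Counseling is the secondary outcome. The analysis is a GEE clustered by clinic, with no baseline covariate named. The balance variables given as examples are clinic size, public/private and rural/urban; baseline testing is not among them.

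**The concern.** Score 2 has the same definition as the primary outcome, measured before randomization. It is the natural variable on which to balance the arms, and it is already in hand. The default scheme balances a transform of it, so two clinics can share a performance score while testing very different proportions of clients. Arms matched on the product can still differ in baseline testing.

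With 12 clinics per arm, such a difference adds noise to the estimated SAIA effect, and no analysis step is named that would take it out again. At stake is the precision of the primary comparison and how easily a reader can interpret a visible baseline difference.

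**Working it through.** The documents state no baseline testing rate, between-clinic spread, balance tolerance or baseline-to-follow-up correlation, so there is no plan figure to reproduce. Steps 1 and 2 are arithmetic on the plan's definition. Steps 3 to 5 rest on assumptions, labelled as such. Write C for counseling (Score 1) and T for testing (Score 2).

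**1. Equal scores, unequal testing.** Score = C × T.
- C = 1.00, T = 0.25 gives 0.25; C = 0.50, T = 0.50 gives 0.25.
- If every tested client was counselled (T ≤ C), a score s allows T from s to √s, a maximum ratio of 1/√s: 5.0 at s = 0.04, 2.24 at 0.20, 2.0 at 0.25, 1.41 at 0.50. A two-fold gap therefore needs a score of 0.25 or lower.

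**2. When the scores track.** If C = T = p, the score is p². Equal mean p² does not give equal mean p. Illustration: clinics at p = 0.20 and 0.60 have mean p² = (0.04 + 0.36)/2 = 0.20 and mean p = 0.40. Two clinics at p = √0.20 = 0.447 also have mean p² = 0.20, but mean p = 0.447. The scores track perfectly, yet mean testing differs by 4.7 points.

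**3. Size of the leftover imbalance.** Simulation of 24 clinics split 12:12. Assumed: baseline testing mean 30%, SD 23 points; counseling mean 39%; C–T correlation 0.7 to 0.9; allocations kept if in the best 20% on volume and best 10% on score.

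| Restriction | SD of arm difference in baseline testing (points) |
|---|---|
| None | 9.2 |
| Volume + product | 3.0 (correlation 0.9) to 4.0 (correlation 0.7) |
| Volume + Score 2 | 0.7 |

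Share of imbalance variance removed by the product: 1 − (4.0/9.2)² = 81% to 1 − (3.0/9.2)² = 89%.

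**4. Effect on the estimate.** With baseline-to-follow-up correlation r across clinics (assumed), equal spread at both times, and no covariate, the variance ratio of product to Score 2 is

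[(1 − r²)·9.2² + r²·sd²] / [(1 − r²)·9.2² + r²·0.7²].

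- r = 0.7: (43.17 + 4.41)/(43.17 + 0.24) = 1.10 for sd 3.0; (43.17 + 7.84)/(43.17 + 0.24) = 1.18 for sd 4.0.
- r = 0.5: (63.48 + 2.25)/(63.48 + 0.12) = 1.03 for sd 3.0; (63.48 + 4.00)/(63.48 + 0.12) = 1.06 for sd 4.0.

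Taking square roots, the standard error is about 2% to 8% larger.

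**5. Sensitivity to other assumptions.** A second simulation used logit-normal T (median about 0.30) and C (median about 0.60), C–T correlation −0.5 to 0.8, and the best 10% of allocations on a joint distance. The 95th percentile of the absolute arm difference in baseline testing was:

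| Restriction | Points |
|---|---|
| None | 11.3–15.5 |
| Volume + product, T ≤ C | 5.0–6.6 |
| Volume + product, testing without counseling possible | 6.9–11.3 |
| Volume + Score 2 | 2.5–3.5 |
| Volume + Score 1 + Score 2 separately | 3.8–5.1 |

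The worst product result, 11.3 points, came from negatively correlated scores with testing possible without counseling. There the SD fell only from 7.74 to 5.74 points, so the product removed 1 − (5.74/7.74)² = 45% of the imbalance variance. That is the divergent case the plan's clause is meant to catch.

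**The case against.** **The product is a default, not a final choice.** The plan explains why it prefers a composite, promises to look at the individual scores if they diverge, and keeps the balance variables open until preliminary data are seen. This stands, and it rules out saying that the plan has simply overlooked baseline testing. What remains is that divergence has no threshold, the adaptation is not described, the Randomization paragraph repeats only the default, and step 2 shows that the clause is silent when the scores track.

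**The two-fold example is the case the clause targets.** This also stands. A reader might infer from step 1 that clinics with two-fold different testing will routinely be treated as equal. The documents do not support that: it is possible only at low scores if T ≤ C, and it requires counseling and testing to move in opposite directions.

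**The issue is not bias.** A reader might also infer that leftover imbalance biases the SAIA effect. It does not. Allocation is random among the acceptable combinations, so the estimate is unbiased over randomizations; the loss is precision and the chance imbalance of a single draw.

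**Counseling is the secondary outcome, so the composite protects both.** This does not hold up. In a further simulation, also with assumed distributions and 10% acceptance, separate constraints on Score 1 and Score 2 gave tighter balance than the product on testing (SD 1.3–2.0 against 2.4–5.4 points) and on counseling (1.6–2.4 against 4.1–7.1 points).

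**Conclusion.** The point holds as a modest loss of efficiency in the default scheme, with an incompletely specified fallback. The mismatch between the balancing score and the primary outcome, the lack of a trigger and the absence of a named baseline covariate come directly from the documents. So does the direction of the effect.

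The size does not. The 3% to 18% increase in variance assumes the distributions and acceptance rules in step 3 and a baseline-to-follow-up correlation of 0.5 to 0.7. It applies where counseling and testing correlate 0.7 to 0.9, which is where the plan's clause would probably not act. A variant that made tested clients a subset of counselled clients gave 2% to 4% at a correlation of 0.5 and 7% to 13% at 0.7. If the scores diverged and the default were kept, the loss would be larger. The trial's validity is not in question.

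**What to change.** **If the allocation has not been drawn.** In Section 5.1 (Randomization), replace the performance score with two separate constraints, HIV Testing (Score 2) and HIV Counseling (Score 1), alongside new client volume, and state a tolerance for each. Both scores are already computed, so this is a change of one line. The cost is slightly looser balance on testing than with Score 2 alone (95th percentile 3.8–5.1 against 2.5–3.5 points in step 5).

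**If it has been drawn.** This is very probably the position, since the disclaimer at the end of Section 5.1 says Aim 2 began in February 2020. Editing the randomization text would then change nothing. Instead:
- report baseline Score 2 by arm, alongside the balance variables in Section 5.2;
- add clinic-level baseline Score 2 as a covariate in the Section 5.2 GEE for the primary outcome;
- state which variables and tolerances the allocation actually used.

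The covariate costs one clinic-level degree of freedom out of 24 clinics. The data are already held.
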